### **9.2.2. Sample Size Sensitivity**

Probability of success (Assurance) was determined for all combinations of these three factors: success thresholds of 0.95, 0.85, 0.8, 0.75 and 0.7, sample sizes (per arm) of 5, 10, 15, 20, 25, 30, 35, 40, 45, 50, 100 and Known % attenuations of 0% to 30% by 2% increments, 35 to 50% by 5% increments and 60% to 100% by 10% increments. Full results are available on file.

### **9.2.3. Sample Size Re-estimation or Adjustment**

No sample size re-estimation is currently planned for this study beyond that described in Section 9.3.2. However, if during the course of the study, new information becomes available about clinically meaningful differences or variability estimates, a sample size re-estimation may be conducted.

## **9.3. Data Analysis Considerations**

### **9.3.1. Analysis Populations**

Subjects who receive at least one dose of study medication will be included in an 'All Subjects' population. Furthermore, subjects in the 'All Subjects' population who have a successful screening sputum sample will be included in the 'Sputum Producers' population.

[figure not shown]
Additionally, subjects from the All Subjects population who were not on Placebo and who provide GSK2245035 pharmacokinetic samples will be included in a 'PK' population.

Other populations, such as a Per-protocol population, may be defined in the RAP.

### **9.3.2. Interim Analysis**

Recruitment into the study would continue whilst the interim analysis is taking place.

The interim analysis will require knowledge of which subjects are in the Placebo arm and determine how many of those Placebo subjects failed to meet the screening inclusion criteria for LAR in their 1 week follow up visit (i.e. did not show three FEV1 decreases of  $\geq 15\%$  relative to saline baseline between 4 and 10 hours, with two FEV1 decreases being at consecutive time points at 1 week follow up). The number of subjects on placebo who do not exhibit an LAR (non-LAR responders) will be determined from the available interim data. This number will be checked against [Table 3](#) to advise whether the study should continue or whether further review of the interim analysis data is required to assess the impact. For example, if at the time the interim analysis occurs 10 subjects were on Placebo and 4 of those 10 did not demonstrate an LAR response then the interim analysis would recommend reviewing the data further.

**Table 3**      **Lookup table for Interim Analysis Decision Pathway**

Assessing impact of non-LAR response rate: To evaluate whether recruiting additional subjects may counteract the impact of the non-LAR responder alternative version(s) of Table 3 would be constructed, but using final sample sizes that range from 20 to 30 subjects per arm. If any of the resulting estimates for probability of success are within 10% of the original operating characteristic the study may continue; but requiring additional subjects (the smallest number that satisfied the continuation criteria). In addition posterior distributions for the percentage attenuation of the primary endpoints by GSK2245035 would be constructed from the available interim data.

Amending protocol / termination of further enrolment (existing subjects would complete the study as planned): If the median (point estimate) for the observed treatment effect is dramatically different to the assumed effect from the AZ study, the study team may wish to predict the probability of success at the end of the study from the interim information (details to be provided in the RAP). If this updated probability of success is low then the study team may review any of the other available data items at the interim prior to amending the protocol / terminating further enrolment (and share these outputs with appropriate internal GSK governance boards / senior management).

To determine the probability of success in the presence of non-LAR responders (for each of the primary endpoints) simulations were performed for each possible combination of number of available placebo subjects (n) and number showing no LAR response (r) using the AZ point estimates as the true percentage attenuation:

The rate of non-LAR response (p) was assumed to be the same for Placebo and GSK2245035 arms. A Beta(0.1, 0.1) prior distribution was assumed for the rate, which was updated using conjugate formulae as Beta( $0.1 + r$ ,  $0.1 + n - r$ ) and a value sampled from this posterior distribution. The number of future subjects on placebo with a non-LAR response was sampled from a Binomial distribution using the sampled value of p and ( $20 - n$ ) observations (the total is a mixture of observed interim data and this sampled value). Similarly the number of non-LAR responders on the GSK2245035 arm was sampled from a Binomial distribution with the same value of p and 20 observations. Each non-responding individual was assigned a constant value for the response, and the collection of non-responders were combined with the collection of LAR responders (generated in a similar way using the random effects meta-analysis to obtain the expected responses). The probability of success was determined for each of the combined datasets and the median was derived. If this median was more than 10% smaller than the original operating characteristic the recommendation is to further review the data. The recommendations from the two endpoints were combined into a single table. Wherever there was disagreement between cells the review data decision was chosen.

Sensitivity analyses showed the outcome of this approach is highly dependent on the value of the constant used for the non-LAR responses (the further the choice from the range of plausible values for LAR responders the more likely the recommendation was to review data). The choice of value is arbitrary in nature, but was selected as -0.45 for Minimum Change From Saline and -0.2 for Weighted Mean Minimum Change From Saline, based upon applying the LAR criteria to seven historical studies and deriving the mean responses of all non-LAR responding subjects. Since the decision tables cover all interim study possibilities and is pre-specified the consequences of this arbitrary choice can be articulated.

### **9.3.2.1. Headline results for LAR endpoints at Follow Up 1**

The following is conditional on the study not being stopped early by the interim analysis. To facilitate internal GSK decision making a data snapshot will be taken when the last subject's BAC FEV1 data (and derived LAR endpoints) from Follow Up 1 are available. The associated planned efficacy outputs (to be provided in the RAP) will be produced from that (unblinded) snapshot and shared internally with the GSK study team and internal GSK governance boards / senior management. This data snapshot will not represent a cleaned and locked database and hence its results will not be formally reported as they will be superseded by the formal end of study results.

## **9.4. Key Elements of Analysis Plan**

### **9.4.1. Primary Analyses**

Statistical models will be fitted separately to each LAR endpoint (weighted mean and minimum FEV1). These parameters will be analysed using analysis of covariance (ANCOVA) with treatment and baseline in the model; other covariates such as centre, allergen exposure ('presumed'/'unknown') (see Section 6.2) and allergen exposure by treatment interaction may be included in the model if the observed data support it (the default position is not to include the model terms involving the stratification factor). Treatment comparisons of GSK2245035 vs Placebo will be presented with results also expressed as percentage attenuations to aid clinical interpretation. The posterior probability of any percentage attenuation will be obtained along with appropriate summary statistics from the posterior distribution (e.g. 95% and 70% equi-tail Credible Intervals).

The principle inferences are expected to come from models with non-informative priors. Sensitivity analyses using informative priors based on AZ data may be fitted.

Full details of the BAC analyses will be provided in the RAP.

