The purpose of the interim analysis is to evaluate whether the non-reproducible LAR rate is reducing the expected probability of success by more than 10% and, if it is, to perform an unblinded review of the observed data to assess the impact and cease further recruitment into the study, or enrol additional subjects to counteract the effects. Simulations were used to quantify the expected reduction in probability of success, using an estimate of the non-responder rate from the placebo arm only. The timing of the interim is linked to the enrolment rates and will be triggered by whichever occurs first i) Approximately 1 year after the first subject successfully completes the Follow Up 1 assessments or, ii) When 28 subjects have successfully completed the Follow Up 1 assessments or iii) At the discretion of the GSK Study Team up to the time that 28 subjects have successfully completed the Follow Up 1 assessment.

- It is hypothesized that TLR7-mediated immunomodulation requires allergen to be present and exposure to aeroallergens may fluctuate or remain relatively constant depending on the allergen, time of year, and a subject's household characteristics or activities. Further, exposure to certain aeroallergens may be presumed and, in other instances, is unknown unless outdoor air and household samples are analyzed. For example, allergen exposure may be presumed if a subject who is sensitized to and challenged with grass pollen enrolls during grass pollen season or whose treatment is expected to coincide with grass pollen season. A subject sensitized to animal epithelia who has that animal in his/her house or has occupational exposure may be presumed to have exposure. These subjects will potentially exhibit a different response to study drug to someone without similar exposure to the allergen. Exposure to certain allergens, particularly perennial allergens (i.e. house dust mite) cannot be presumed and will be considered unknown for the purposes of this protocol. Therefore, the allergen a subject is administered for the BAC will need to be considered according to whether the subject has exposure to that allergen outside of the challenge. Consequently, the randomization will be stratified by 'presumed' and 'unknown' exposure to allergen in addition to stratification by centre.

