## 6.2. Treatment Assignment

Subjects will be assigned to one of two treatments (either 20 ng GSK2245035 or placebo), in accordance with the randomization schedule generated by Clinical Statistics, prior to the start of the study, using validated internal GSK software RandAll NG. The randomisation will be stratified by centre and also by exposure state during the treatment phase to the allergen selected for BAC (two strata – “Presumed” and “Unknown”). See Section 4.4 for further details regarding allergen exposure.

It is planned that an Interactive Response Technology (IRT) will be used in this study to assign randomization and drug containers. It can also be used to emergency unblind subjects if required (see Section 6.3).

Once assigned to a subject a randomization number may not be re-used.

More details of how and when a subject is allocated a randomization number and the subject numbering convention will be given in the Study Reference Manual (SRM).

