### **9.2. Sample Size Considerations**

The following was performed for each of the proposed LAR primary endpoints:

[figure not shown]
- Success criteria: declare endpoint success if the posterior probability of any treatment attenuation exceeds 0.7.
- The probability of declaring a success has been computed for a range of true percent attenuations and sample sizes (n per arm equal allocation). To make the figures easier to interpret the “nuisance” parameters of the placebo response and the standard deviation have been accounted for as follows:
- Eight previous GSK BAC studies (Crossover design) have been re-analysed to obtain estimates of the average placebo response and the associated estimate of residual variability applicable to the proposed Parallel Group design.
- These estimates were combined in a random effects meta-analysis to obtain posterior distributions for the underlying parameter values (placebo average response, residual variability (for an individual subject) and a between study variance component). The future placebo response was computed as the sum of random draws from the posterior distributions of the placebo average response parameter and a normal distribution with mean zero and variance equal to the between study variance parameter. The future GSK2245035 response was derived using the simulation scenario’s true percentage attenuation. A pooled sample variance value was generated using a Chi-Square distribution with degrees of freedom appropriate to the simulation scenario and a sampled variance from the meta-analysis posterior distribution. Those numbers were entered into the standard formulae for power curves. Repeating this process 10,000 times and taking the median of the resulting power values constructs “Assurance” operational characteristics for the combination of true percent attenuation and sample size under evaluation.

- These assurance operational curves have been summarised graphically. The x-axis is a hypothetical true drug effect that is assumed to be known for experimental design purposes.
- The simulations can also be used to compute the minimum observed percentage attenuations that would result in a successful study outcome. The median (of the 10,000 simulations) have been derived for a variety of sample sizes and success criteria (probability thresholds 0.7, 0.75, 0.8, 0.85, 0.95) and displayed graphically. The y-axis is the observed effect from the study data.

[figure not shown]

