**Table 2 Input data for Sample Size Work**

GSK Internal Study ID	LAR Minimum FEV1 between 4-10h			LAR Weighted Mean FEV1 between 4-10h		
	Average Placebo Response	Degrees of Freedom	Residual Variability	Average Placebo Response	Degrees of Freedom	Residual Variability
PPD	-1.3975	33.5	0.40571	-0.9462	33.1	0.30417
	-1.0864	45.9	0.13063	-0.7093	42.3	0.11430
	-1.1238	22.9	0.30521	-0.6916	22.8	0.18820
	-0.9006	48.9	0.07344	-0.3749	47.9	0.02191
	-0.7309	85.3	0.10717	-0.4662	84.4	0.07528
	-0.9027	31.9	0.27740	-0.5502	34.0	0.20925
	-1.4484	20.4	0.40528	-0.9817	20.3	0.31342
	-0.8129	69.6	0.15866	-0.5260	71.8	0.08695

Assuming the true treatment effect of GSK2245035 is no worse than the results from the AstraZeneca study and 20 subjects complete follow up assessments the probability of meeting the success criteria for Min LAR and WM LAR are approximately 78% and 81% respectively. This is considered sufficient justification for requiring 20 completers.

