To evaluate whether recruiting additional subjects may counteract the impact of the non-LAR responders alternative version(s) of [Table 1](#) were constructed using the same methodology, but using final sample sizes that range from 20 to 30 subjects per arm. At each cell, if the probability of success was within 10% of the original operating characteristic for that endpoint (i.e. the characteristics derived under the assumption of zero non-LAR responders) the study would continue; but requiring additional subjects (the smallest number that satisfied the continuation criteria). These additional tables have been compressed into [Table 2](#), which shows the smallest number of subjects (per arm) required to continue the study (if the continuation criteria were still not met with 30 subjects per arm the cell is flagged as recommending further data review).

Table 2 Lookup Table for Interim decision and revised sample sizes (per arm)

Additional analyses / outputs to support the interim analysis decision making

Equivalent versions of the planned summary statistics and figures supporting the primary endpoint/analyses.

Posterior distributions for the percentage attenuation of the primary endpoints (WM and Minimum LAR at FUV1) by GSK2245035 would be constructed from the available interim data using the same methodology as for the planned final analysis; except that a simplifying assumption will be used and terms relating to allergen exposure in the model will be excluded; since there may not be enough information in each strata at the time of the interim to facilitate their estimation (see Section 7 for details of the planned Primary analysis).

Non-binding “Rule of thumb” for amending protocol/termination of further enrolment (existing subjects would complete the study as planned)

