For each treatment arm the (joint) posterior predictive distribution of an individual subject's primary endpoints will be obtained (separate Variance Covariance (VCV) matrices for each treatment arm are preferred to cover the case where variability is also a function of treatment; but there may not be sufficient information in the interim dataset to estimate the required parameters, in which case a pooled VCV matrix across treatment arms would be acceptable). The predictive distributions will be used to simulate a sufficient number of future subjects to achieve the end of study sample size (planned to be 20 per arm, but may be revised upwards to a value between 21 and 30 per arm depending on the observed placebo non-LAR responder rates). Summary statistics (sample mean and sample variance covariance matrix) will be derived using each set of simulated subjects for each treatment. These summary statistics are used as informative prior distributions for the treatment parameters in models fitted to the observed interim data (with the simplifying assumption that these models exclude allergen exposure covariate(s)). If the resulting posterior probability of any attenuation exceeds 0.7 (for either endpoint) the hypothetical end of study result is a success. By repeating the process of simulating sets of future subjects (10,000 times); producing informative priors for the treatment parameters from those simulated subjects and combining with the (unchanging) observed interim dataset in a model to evaluate individual study success an expected probability of a successful outcome can be obtained if the study were allowed to continue past the interim (i.e. the number of simulated sets flagged as successful / total number of simulated sets of subjects).

The advantage of utilising posterior predictive distributions is that they also account for the uncertainty in the true values of the parameters (caused by having to estimate them using only the interim data). Note: Each simulated subject can be thought of as being generated using the average of each of the covariate values. Therefore sample statistics are used as priors for the treatment related parameters only in the subsequent modelling step. This avoids having to generate covariate values for the simulated subjects (e.g. assign them to a centre, or generate a baseline response for them).

Further details are given below:

Interim Analyses to estimate end of study success

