- Active: Sample Mean Vector $\begin{bmatrix} \bar{x}_1 & \bar{x}_2 \end{bmatrix}_{Act}$ Sample VCV $\begin{bmatrix} S_{WM}^2 & S_{WM}S_{Min} \\ S_{WM}S_{Min} & S_{Min}^2 \end{bmatrix}_{Act}$

Interim Analyses to estimate end of study success
--

- In the statistical model fitted to the WM endpoint the priors are:

$$\hat{\mu}_{P,WM} \sim N\left(\bar{x}_{1,Pbo}^{WM}, \frac{S_{WM,Pbo}^2}{Nrem_{Pbo}}\right), \quad \hat{\mu}_{A,WM} \sim N\left(\bar{x}_{1,Act}^{WM}, \frac{S_{WM,Act}^2}{Nrem_{Act}}\right)$$

- In the statistical model fitted to the Min endpoint the priors are

$$\hat{\mu}_{P,Min} \sim N\left(\bar{x}_{2,Pbo}^{Min}, \frac{S_{Min,Pbo}^2}{Nrem_{Pbo}}\right), \quad \hat{\mu}_{A,Min} \sim N\left(\bar{x}_{2,Act}^{Min}, \frac{S_{Min,Act}^2}{Nrem_{Act}}\right)$$

Step 3: Fit model and flag success or failure
--

- To facilitate easy use of the prior distributions a re-parameterized version of Primary analysis Model M3 can be used (Intercept term removed and the zero constraint on the 2nd treatment level removed).
- Separate models will be fitted to each of the endpoints (WM and Min)
- If the posterior probability that $\hat{\mu}_P < \hat{\mu}_A$ exceeds 0.7 (using the informative prior from the ith MCMC iteration) then the ith MCMC iteration is flagged as resulting in a successful end of study result.
- The overall probability of success is the number of successful MCMC iterations / total number of MCMC iterations

Technical details for deriving the individual tables contributing to [Table 2](#)

To determine the probability of success in the presence of non-LAR responders simulations were performed for each possible combination of number of available placebo subjects (n) and number showing no LAR response (r) using the AZ point estimates as the true percentage attenuation (separate procedure for each of the primary endpoints):

Let K represent the number of subjects per arm to be evaluated with each value of K producing a different table and K ranging from 21 to 30 by 1.

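### The primary LAR model is chosen after treatment-coded outcomes are seen, and if the interaction model M1 is chosen no effect is named for the 0.7 criterion

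*Protocol*

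**What the plan says.** Design. Protocol 6.2 states that "The randomisation will be stratified by centre and also by exposure state during the treatment phase to the allergen selected for BAC". Protocol 4.4 gives the reason, saying of subjects with presumed exposure: "These subjects will potentially exhibit a different response to study drug to someone without similar exposure to the allergen".

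Model. Protocol 9.4.1 has treatment and baseline in the model, with exposure and exposure-by-treatment terms "included in the model if the observed data support it (the default position is not to include the model terms involving the stratification factor"). SAP 7.1.2 Step 1 fits three nested models to each LAR endpoint and selects one:

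- M1: centre, treatment, exposure, treatment-by-exposure, baseline.
- M2: M1 without the interaction.
- M3: M2 without exposure.

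Selection uses DIC changes plus expert judgement. SAP 11.9.1 lets judgement overrule DIC. SAP 11.11.1 takes the simpler model when the DIC difference is below 1, leaves the range from 1 to 2.5 open to consideration, and labels all of this as guidance that the study statistician may override in the light of the observed data. Step 2 optionally adds further covariates from an open list.

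Reporting. SAP 7.1.2 and 11.9.1 require output from all three models in a listing (Listings 42 and 43 in SAP 11.13.16), but SAP 11.9.1 draws summary tables and figures from the chosen model only. If M1 is final, SAP 7.1.2 presents treatment comparisons within each exposure level.

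Criterion. Protocol 9.2 says to "declare endpoint success if the posterior probability of any treatment attenuation exceeds 0.7". On that basis Protocol 9.2.1 reports that "the probability of meeting the success criteria for Min LAR and WM LAR are approximately 78% and 81% respectively". SAP 7.1.2 does not restate 0.7. SAP 3.1 uses it in the interim projection ("If the resulting posterior probability of any attenuation exceeds 0.7 (for either endpoint) the hypothetical end of study result is a success"), where "terms relating to allergen exposure in the model will be excluded" and "a re-parameterized version of Primary analysis Model M3 can be used".

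**The concern.** Treatment is in every candidate model, so the DIC values cannot be computed without treatment codes. The choice is therefore made with outcomes by arm in view. No passage says this in so many words, but it follows from the model forms, and the sponsor is open. The SAP synopsis puts final-analysis decisions before database freeze. That does not make them blind, because interim and headline outputs come from unblinded data before the freeze.

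The 0.7 criterion needs one posterior probability per endpoint. M2 and M3 supply one; M1 supplies two, one per exposure stratum. No passage says whether one stratum, both, or an average must exceed 0.7. At stake is whether the quantity that justified 20 completers per arm can be read off the final analysis without a further choice made after seeing the result. The gap is widest where exposure modifies the response, which is the case Protocol 4.4 raises.

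**Working it through.** **1. The plan's own figure.** Inputs:

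- Table 2 of the Protocol, weighted by degrees of freedom and reading residual variability as a variance: placebo response -0.959 (minimum) and -0.591 (weighted mean); variance 0.188 and 0.130.
- Attenuation of 18% and 27%, and 20 per arm (Protocol 9.2).
- Threshold 0.7, so z = 0.524.

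Formula: success probability = Φ(δ / (σ√(2/20)) - 0.524).

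- Minimum: δ = 0.18 × 0.959 = 0.173; σ = √0.188 = 0.434; Φ(1.259 - 0.524) = 0.77, against 78% stated.
- Weighted mean: δ = 0.27 × 0.591 = 0.160; σ = √0.130 = 0.361; Φ(1.400 - 0.524) = 0.81, against 81% stated.

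Both stated figures are reproduced with a single overall effect per endpoint. The standardised effects are 0.173/0.434 = 0.40 and 0.160/0.361 = 0.44; 0.41 SD is used below.

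**2. How far the reading matters if M1 is used whatever the DIC says.** With no effect and the two strata treated as independent, success is 1 - 0.7² = 0.51 if either stratum counts and 0.3² = 0.09 if both must. With a common effect of 0.42 SD, simulation gives about 0.88 and 0.40-0.44.

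**3. How often it arises.** For a normal linear model with flat priors and n = 40, the closed-form DIC penalty is 2.09 from M3 to M2 and 2.12 from M2 to M1, against 2 for AIC, so the SAP's AIC approximation holds. Simulation: 20 per arm, 20,000 runs per setting, flat-prior t posteriors, DIC guide with no override. Assumed: presumed/unknown splits of 50/50, 80/20 and 20/80; stratum main effect 0 to 0.5 SD; baseline slope 0.65 SD; centre omitted. Because the SAP leaves DIC differences of 1 to 2.5 open, both boundaries are shown.

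| Difference between stratum effects | M1 picked, within 1 | M1 picked and strata on opposite sides of 0.7, within 1 | M1 picked, within 2.5 | M1 picked and opposite sides, within 2.5 |
|---|---|---|---|---|
| None | 6-8% | 5-7% | 3-4% | 2-4% |
| 0.41 SD | 9-15% | 6-14% | 5-8% | 3-8% |
| 0.82 SD | 20-34% | 13-32% | 12-22% | 8-21% |

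The opposite-sides columns are shares of all trials. Given that M1 is picked, 66-97% split across 0.7. A separate simulation with AIC for DIC, 25% or 50% presumed and no interaction gave M1 in about 6% of trials and a split in 5-6%.

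**4. Effect on the success probability** (mean effect 0.41 SD, within-1 rule; fixed M2 gives 0.76-0.78).

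- Difference 0.41 SD: 0.79-0.81 if either stratum counts, 0.67-0.73 if both must.
- Difference 0.82 SD: 0.81-0.85 and 0.52-0.68.

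**5. False success with no effect** (nominal 0.30, within-1 rule).

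- Fixed M2 0.297-0.307; fixed M3 0.294-0.303.
- DIC choice, M2's effect read when M1 is picked: 0.297-0.308.
- DIC choice, either stratum 0.331-0.348; both strata 0.276-0.289.
- Step 2 with three noise covariates (6,000 runs): 0.309 taking the lowest DIC, 0.351 if judgement takes the most favourable model within 2.5, against 0.303 for fixed M2.

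**6. M2 against M3.** Their 0.7 verdicts differ in only 0.4-2.3% of trials.

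**7. An exposure stratum present in one arm only.** M2 stays estimable. If k subjects in that stratum all fall in one arm of 20, the squared correlation with treatment is k/(40 - k), and the SE ratio to M3 (ignoring baseline) is 1/√(1 - k/(40 - k)): √(39/38) = 1.01 for k = 1 and √(37/34) = 1.04 for k = 3.

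**The case against.** The best defence is that the final analysis issues no verdict. No formal hypothesis is tested, the aim is estimation, and SAP 7.1.2 displays posterior probabilities and intervals rather than a pass or fail. The only SAP use of 0.7 is the interim projection, where the model has no exposure terms and the effect is unambiguous. The discretion also leans one way: the Protocol default leaves exposure out, small DIC differences go to the simpler model, and SAP 11.9.1's first example of judgement is rejecting M1 even when DIC favours it. The no-override figures do not reflect that. The largest figures need a stratum difference twice the mean effect, which with equal strata puts the whole effect in one stratum. There, a pooled effect is arguably the less informative summary.

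Most of this stands, and it limits the point to an ambiguity. It does not close it: 0.7 is the basis of the sample size and of the interim definition of an end-of-study success, and a listing of three models shows the choice without saying which result counts.

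Four stronger readings are tempting and not supported:

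- That Protocol and SAP conflict. Protocol 9.4.1 allows the terms if the data support them, so the SAP procedure is broadly consistent with it.
- That the overall result is hidden under M1. M2 and M3 output is still listed.
- That error is inflated. False success stays near 0.30 unless an either-stratum reading, or the most favourable Step 2 model, is chosen.
- That the interim rule already settles the M1 case by accepting either. That word refers to the two endpoints, not the two strata.

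**Conclusion.** The point holds as a gap in pre-specification. The primary LAR model is selected from treatment-coded outcomes by a guide that can be overruled, and under M1 no effect is named for the criterion that supports the 78% and 81%. Under the within-1 rule without override, the criterion is undetermined in roughly 5-7% of trials with no interaction and 13-32% at a 0.82 SD stratum difference. A 2.5 boundary lowers these to 2-4% and 8-21%. The figures rest on the assumed stratum splits, stratum effect and baseline slope, with centre omitted; override could move them either way, though the stated guidance leans down. The consequence is an undetermined and discretionary reading in an exploratory study. It should be corrected because the correction is cheap and the ambiguity is largest in the situation the stratification was designed for.

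**What to change.** Before any unblinded FUV1 data are reviewed, including at the interim:

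- In SAP 7.1.2, name M2 (centre, treatment, allergen exposure, baseline) as the primary model for both LAR endpoints, and its overall treatment effect as the one compared with 0.7. M2 is preferred because it carries the randomisation stratum.
- Use M3 only if M2 does not converge. An exposure stratum with no subject in one arm does not by itself require it.
- Report M1 as the pre-specified interaction analysis, and Step 2 models as sensitivity analyses only.
- Amend the sentence in Protocol 9.4.1 to match.

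The cost is wording plus one model degree of freedom (40 subjects less 4 fixed terms leaves 36), with an SE increase of about 1% to 4% in the one-sided stratum cases above. The EAR analyses would inherit the change, since SAP 8.1.2 refers back to 7.1.2.

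Naming M3 and its treatment effect instead would also close the gap. It needs no protocol change, because M3 is already the Protocol default and the interim form, and the two verdicts rarely differ.
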